#### **7.1.4. Adverse Events of Special Interest (AESI)**

At each Study visit, the Investigator (or designee) will specifically query for any adverse events of special interest (AESI). The following events are considered AESIs for this Study:

- Suspected or confirmed intestinal perforation
- Complicated herpes zoster (multi-dermatomal, disseminated, or with ophthalmic or CNS involvement)
- Malignancy excluding non-melanoma skin cancer
- Non-melanoma skin cancer
- Serious infection (e.g., that requires hospitalization or intravenous antimicrobials)
- Opportunistic infections
- Thromboembolic disease (e.g., deep vein thrombosis (DVT), pulmonary embolism)
- Clinical laboratory abnormalities of concern (Refer to Section 7.2)
- Major cardiovascular event (e.g., myocardial infarction or cerebrovascular accident)

All AESIs, except for non-melanoma skin cancers and mono-dermatomal herpes zoster, must be reported to TBPH Clinical Safety and Pharmacovigilance within 24 hours of the time the Investigator or his/her designee becomes aware of an AESI (Refer to Section 7.1.4). Except for non-melanoma skin cancer that has been fully resected, mono-dermatomal herpes zoster, and certain laboratory abnormalities that are deemed by the investigator to not place subjects at immediate safety risk, all of these AESIs should lead to discontinuation of the study drug. For each of these AESI, an additional targeted questionnaire needs to be completed to assess for risk factors. For thromboembolic events in particular, the subject should undergo evaluation for hypercoagulable state (e.g., with clinically relevant investigations, such as referral to a specialist and/or blood testing for a predisposition to a hypercoagulable state) and repeat imaging to assess resolution of the finding.

Besides these AESI, for other AEs, study drug may be interrupted and resumed as deemed medically appropriate by the investigator (e.g., during an infection that requires oral antimicrobial treatment).

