## 7.2. Clinical Laboratory Abnormalities and Other Abnormal Assessments as Adverse Events or Serious Adverse Events

Abnormal laboratory findings (such as clinical chemistry, hematology, or urinalysis) or other abnormal assessments (such as electrocardiograms [ECGs], X-rays, or vital signs) that are associated with signs and/or symptoms or are considered clinically significant in the judgment of the investigator must be recorded as AEs or SAEs if they meet the definition of an adverse event (or serious adverse event), as described in Section 7.1.1 (Adverse Event) and Section 7.1.2 (Serious Adverse Event).

Clinical laboratory abnormalities of concern may include, but are not limited to, the following where the investigator must recheck within 2-7 days, except for AST or ALT > 3x ULN where these need to be rechecked within 48-72 hours, as deemed appropriate by the investigator:

- clinically significant reduction in neutrophils or leukocytes or lymphocytes that may place subjects at higher risk for infection such as:
  - moderate or severe neutropenia (e.g., absolute neutrophil count of < 1.0 x 10^9/L)
  - moderate or severe leukopenia (e.g., white blood cell count of < 2.0 x 10^9/L)
  - moderate or severe lymphocytopenia (e.g., absolute lymphocyte count of < 0.5 x 10^9/L)
- abnormal hepatic panel (AST or ALT > 3x ULN)
- an excessive decrease in creatinine clearance [e.g., a reduction by ≥ 50% from baseline (baseline for this purpose is defined as creatinine clearance calculated for Day 1, predose activities)]

Depending on the subject's baseline and individual scenario, the investigator should report as an AESI and stop study drug treatment if any of the below is seen:

- moderate or severe neutropenia (e.g., absolute neutrophil count of < 1.0 x 10^9/L) on two sequential laboratory reports
- moderate or severe leukopenia (e.g., white blood cell count of < 2.0 x 10^9/L) on two sequential laboratory reports
- moderate or severe lymphocytopenia (e.g., absolute lymphocyte count of < 0.5 x 10^9/L) on two sequential laboratory reports
- a reduction by ≥ 50% from baseline in creatinine clearance on two sequential laboratory reports
- ALT or AST > 8x ULN on a single laboratory report. Note: See [Appendix 6](#) for an algorithm of evaluating and managing subjects with ALT or AST > 3x ULN.

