### **8.6.3. Laboratory Data**

Safety laboratory values and C-reactive protein values, changes from baseline, values relative to normal ranges, and clinical laboratory abnormalities of concern will be summarized by visit, overall and by arm. C-reactive protein, [REDACTED] total cholesterol, LDL, HDL, and triglycerides levels will be log-transformed for summarization.

Reference ranges provided by the laboratory for each test will be used to evaluate the clinical significance of laboratory test results. Values falling outside the relevant reference range will be flagged, as appropriate, in the data listings. Clinical laboratory abnormalities of concern will be listed in a separate listing. A listing of pregnancy test results will be provided.

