3.4. Safety Analyses

The analysis of safety data includes an overall summary of adverse event preferred terms by body/organ system, drug exposure (duration of treatment), dosing information/compliance, clinical laboratory results, vital signs and ECGs. Tables summarizing the adverse events reported by subjects who died, experienced non-fatal serious adverse events (SAE), or prematurely discontinued the study due to adverse event (AEs) will be prepared. Summaries of potentially clinically notable laboratory results and vital sign abnormalities are presented.

Inferential statistical tests will not be performed for adverse event incidence rates.

For all safety analyses, the safety analysis population will be used.

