3.4.3. Additional Safety Assessments

3.4.3.1. Clinical Laboratory Parameters

Laboratory data, hematology, serum chemistry and urinalysis, will be summarized in terms of observed values and changes from baseline. In addition, changes from baseline relative to normal ranges from the central lab (e.g., shifts from normal to abnormal high/low) will be summarized.

The number and percentage of subjects with clinically abnormal lab values will also be summarized by timepoint for the following criteria:

- absolute neutrophil count of $< 1.0 \times 10^9/L$

- white blood cell count of $< 2.0 \times 10^9/L$
- absolute lymphocyte count of $< 0.5 \times 10^9/L$

A listing of all abnormal lab values will be provided.

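### SAP 3.4.3.1 counts subjects for three of the five laboratory abnormalities named in protocol 7.2; the liver-enzyme and creatinine-clearance counts are left out and the omission is not described

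*SAP*

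**What the plan says.** Protocol 8.6.3 commits to a table: "clinical laboratory abnormalities of concern will be summarized by visit, overall and by arm". Protocol 7.2 gives the content of that category in an open list. Besides the three white-cell criteria, the list names "abnormal hepatic panel (AST or ALT > 3x ULN" and "an excessive decrease in creatinine clearance [e.g., a reduction by ≥ 50% from baseline". For the last of these it fixes the reference value: "baseline for this purpose is defined as creatinine clearance calculated for Day 1, predose activities".

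SAP 3.4.3.1 introduces its threshold counts with "The number and percentage of subjects with clinically abnormal lab values will also be summarized by timepoint for the following criteria" and then lists only the neutrophil, white-cell and lymphocyte cut-offs. The same section plans observed values, changes from baseline, shifts relative to the normal range, and a listing of abnormal values. SAP 3.4 adds a general promise, "Summaries of potentially clinically notable laboratory results and vital sign abnormalities are presented", but gives no further laboratory criteria.

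Protocol 8.1 says that the SAP will describe changes to protocol-specified analyses. SAP section 1 and SAP Appendix 1 name only the efficacy analyses as dropped. Other dropped items, such as enrollment (SAP 3.2.1) and subgroups (SAP 3.5.2), are marked as not applying to the synoptic report.

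**The concern.** Changes in laboratory safety tests are part of the primary endpoint (protocol synopsis, Study Endpoints). Protocol 1.5 lists liver function tests and serum creatinine among the values altered in patients on a systemic JAK inhibitor, and it says that kidney and liver function will be monitored. The SAP keeps the blood-count part of the planned table and loses the liver and kidney parts.

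If the SAP is followed as written, the report will not say how many subjects at each visit had AST or ALT above 3x ULN, or how many lost half their creatinine clearance. A reader who wanted those numbers would have to build them from subject listings and, for clearance, compute the quantity first. The synoptic format does not explain the gap: SAP section 1 says that the synoptic report includes the safety endpoints, and it gives the format as a reason for dropping efficacy only.

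**Working it through.** No sample size, power or error rate is involved, so the check is a comparison of texts followed by a short calculation of what the remaining tables can show.

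**1. Criteria side by side.**

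| Protocol 7.2, first list | Count in SAP 3.4.3.1 |
|---|---|
| Neutrophils < 1.0 x 10^9/L | Yes, same cut-off |
| White cells < 2.0 x 10^9/L | Yes, same cut-off |
| Lymphocytes < 0.5 x 10^9/L | Yes, same cut-off |
| AST or ALT > 3x ULN | No |
| Creatinine clearance down by >= 50% | No |

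Five are named and three are carried over, so 5 - 3 = 2 are missing. The identical cut-offs suggest that the SAP list was taken from this protocol list.

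**2. Is the gap filled or described elsewhere in the SAP?** SAP 5.2.1 derives study day, change from baseline and BMI, but not creatinine clearance. Clearance is not a measured analyte in the chemistry panel (protocol 6.4.1.13), so no table or listing will contain it unless it is derived. No statement in the SAP says that the two counts are dropped.

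**3. What the shift table shows for liver enzymes.** Subjects with normal ALT at baseline who reach 1.1x, 3.1x and 10x ULN all fall in the same normal-to-high cell.

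**4. What the creatinine tables show for clearance.** Protocol Appendix 2, for a male: clearance = (140 - age) x ideal weight / (72 x creatinine), with ideal weight = 50 + 2.3 x (height in cm - 152.4) / 2.54. With age and height unchanged, a 50% fall is a doubling of creatinine. Take as an illustration a man aged 40, 175 cm tall:

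- ideal weight = 50 + 2.3 x 22.6 / 2.54 = 70.46 kg
- clearance = 100 x 70.46 / (72 x creatinine)

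The documents give no ULN for creatinine. An assumed range of 1.0 to 1.3 mg/dL gives:

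| Creatinine, mg/dL | Clearance, mL/min | Change | Criterion | Rise, mg/dL | Normal-to-high shift |
|---|---|---|---|---|---|
| 0.5 to 1.0 | 195.7 to 97.9 | -50.0% | Met | 0.5 | None at any ULN in the range |
| 0.8 to 1.4 | 122.3 to 69.9 | -42.9% | Not met | 0.6 | Yes, throughout |
| 0.8 to 1.6 | 122.3 to 61.2 | -50.0% | Met | 0.8 | Yes, throughout |

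A doubling produces no normal-to-high shift only when baseline creatinine is at or below half the ULN, that is 0.50 to 0.65 mg/dL over the assumed range. Above that a shift appears, but rows 2 and 3 show that it does not separate subjects who meet the criterion from those who do not. Rows 1 and 2 show that the size of the absolute change does not do so either: the larger rise is the one that fails the criterion.

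**5. What the AESI table shows.** Protocol 7.1.4 defines the laboratory category as "Clinical laboratory abnormalities of concern (Refer to Section 7.2", which takes in the whole of 7.2. The second list in 7.2 is narrower and opens with "the investigator should report as an AESI and stop study drug treatment if any of the below is seen"; most of its items need repeat results or a combination of findings. Under either reading the table counts what investigators reported, and SAP 3.4.2.1 presents it by category and preferred term, not by visit.

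**6. Rechecks.** Protocol 7.2 calls for a recheck within 2 to 7 days, or 48 to 72 hours for AST or ALT above 3x ULN. SAP 3.1.3 uses the visit named on the CRF, and SAP 3.1.4 takes the latest laboratory result for that visit. A recheck entered under the same visit would therefore replace the qualifying value. If it is entered as unscheduled, SAP 3.1 keeps it out of the summaries and the qualifying value stays.

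**The case against.** The strongest reply is that these abnormalities would still be visible. The default summary in SAP 3.1 includes the maximum, so an ALT of 10x ULN selected for a visit can show as that visit's maximum. If the maximum is below 3x ULN, the reader can infer a zero count. Percent change is already defined (SAP 5.2.1.2), and a doubling of creatinine is nearly the same thing as the clearance criterion. Raised enzymes recorded as adverse events enter the TEAE tables. All results are listed. The study stopped early and is reported descriptively, and the separate table specifications may hold criteria that the SAP text does not.

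Most of this stands as a limit on the harm. It does not supply the counts. A maximum describes one subject, not how many crossed the line. SAP 3.4.3.1 plans changes from baseline and does not ask for percent change in creatinine. Adverse event entries depend on investigator judgment. The table specifications are not part of the SAP text, which names three criteria.

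It is also fair to say that one row for values above 3x ULN still pools 3.1x with 10x. The proposal restores the threshold that the protocol names; it is not a graded liver table. The clearance example rests on an assumed ULN and a high baseline clearance, and nothing in the documents shows that such a subject is likely.

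**Conclusion.** The point holds. Two of the five named criteria have no subject count, the SAP has no derivation for one of them, and the omission is not described as protocol 8.1 requires. It should be corrected because it concerns the primary safety endpoint and the correction is cheap. It does not affect the validity of any other planned summary.

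Three stronger readings are tempting and are not supported:

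- A reader might infer that liver or kidney signals would be hidden. They would not: the partial cover above is real. What is missing is the number of subjects at the protocol's thresholds.
- A reader might infer that the counts were removed on purpose. The documents are silent on the reason, and an oversight fits equally well.
- A reader might infer that the latest-result rule will erase abnormal values. That happens only if a recheck is entered under the same visit. The three existing counts are all low thresholds, so what could be lost from them is a low value, not a high one.

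The conclusion assumes that the unseen table specifications follow the SAP text. Five is the number of examples named in an open list, not a complete set. How many subjects met either missing criterion cannot be known from the documents; it may be few or none, and a stated zero would still be informative.

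**What to change.** In SAP 3.4.3.1 add the number and percentage of subjects, by visit, overall and by arm, with:

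1. AST or ALT above 3x ULN;
2. a fall of at least 50% in creatinine clearance from the Day 1 pre-dose value, or from the 0157 value that stands in for it under schedule footnote a.

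Add the protocol Appendix 2 formula to the derivations. It needs height, which is not in the LTS schedule but is already summarized under SAP 3.2.3; carry it from the 0157 data where needed. If either count is deliberately left out, say so in the SAP and give the reason.

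As a secondary step, state that all five threshold counts use any valid result recorded under the visit, with invalid or erroneous results excluded in line with SAP 5.2.2.4. One selection rule then applies to the whole table, and a recheck entered under the same visit cannot remove a qualifying value. This is an exception to SAP 3.1.4 for these counts only.

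The cost is one derivation, a few table rows with matching entries in the table specifications, and a few sentences of SAP text. No new data collection is needed, and no clinical threshold changes.

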## **8. STATISTICAL CONSIDERATIONS**

### **8.1. General Considerations**

All individual data will be listed as measured. All statistical summaries and analyses will be performed using [REDACTED]

Continuous data will be summarized using an 8-point descriptive summary (*n*, mean, standard deviation, median, interquartile range [25% quartile, 75% quartile]), minimum, and maximum) or a 7-point descriptive summary (*n*, mean, SD, coefficient of variation [CV], median, minimum, and maximum) unless otherwise specified.

Categorical data will be summarized using counts and percentages. Percentages will be shown to 1 decimal place and percentages for zero counts will be omitted.

The Statistical Analysis Plan (SAP) and the table, figure, and listing shells will be finalized prior to database lock. Any changes to protocol-specified analyses will be described in the SAP.

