5. SUPPORTING DOCUMENTATION

5.1. Appendix 1: Changes to Protocol-Planned Analyses

The protocol-planned efficacy analyses are not required for the synoptic CSR.

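### The SAP's laboratory threshold table leaves out the protocol's liver and kidney criteria without saying so, and its counts depend on how a recheck is labelled

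*SAP*

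**What the plan says.** Protocol 8.6.3 states that "clinical laboratory abnormalities of concern will be summarized by visit, overall and by arm". Protocol 7.2 gives the term its content: "Clinical laboratory abnormalities of concern may include, but are not limited to, the following where the investigator must recheck within 2-7 days". AST or ALT above 3x ULN is the exception, "where these need to be rechecked within 48-72 hours". The section then names neutrophils below 1.0, white cells below 2.0 and lymphocytes below 0.5 (all x10⁹/L), AST or ALT above 3x ULN, and "an excessive decrease in creatinine clearance", illustrated by a drop of at least 50% from baseline. Protocol 8.1 adds: "Any changes to protocol-specified analyses will be described in the SAP".

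SAP 3.4.3.1 reads "The number and percentage of subjects with clinically abnormal lab values will also be summarized by timepoint for the following criteria" and lists neutrophils, white cells and lymphocytes at the same thresholds. The SAP's record of changes (Appendix 1) consists of one sentence: "The protocol-planned efficacy analyses are not required for the synoptic CSR".

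Three general SAP rules decide which results reach the table:
- Section 3.1 restricts summaries to scheduled or windowed visits. Unscheduled results are listed only.
- Section 3.1.3 assigns a result to the visit named on the CRF and defines no window.
- Section 3.1.4 selects the latest laboratory result when a visit has more than one.

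**The concern.** Safety is the only primary objective. Protocol 1.5 names liver tests and serum creatinine, along with falling blood counts, among the changes seen with a systemic JAK inhibitor. The form that SAP 3.4.3.1 uses for blood counts, a number and percentage past a stated threshold, is read straight from the laboratory data and does not wait for an investigator to decide that a value is reportable. The plan provides this for haematology and not for liver or kidney, and it gives no reason.

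The selection rules raise a second problem. A count of threshold crossings should not change with how a site labels a repeat sample. Protocol 7.2 requires a repeat after exactly the values that this table is meant to count.

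**Working it through.** **1. The two lists side by side**

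| Abnormality named in Protocol 7.2 | In SAP 3.4.3.1? |
|---|---|
| Neutrophils < 1.0 x10⁹/L | Yes |
| White cells < 2.0 x10⁹/L | Yes |
| Lymphocytes < 0.5 x10⁹/L | Yes |
| AST or ALT > 3x ULN | No |
| Creatinine clearance fall ≥ 50% from baseline | No |

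Result: 3 of 5 named criteria, and 0 of 2 for liver and kidney.

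**2. Is the omission declared?** Appendix 1 covers efficacy only. Elsewhere the SAP marks dropped sections as not applicable to the synoptic report (for example 3.2.1 Enrollment and 3.5.2 Subgroup Analyses). Section 3.4.3.1 carries no such mark.

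**3. Does another output supply the count?**
- *AE and AESI tables.* Entry depends on the investigator's judgement. The instruction in 7.2 to report an AESI is attached to a stricter list. A single ALT of 6x ULN that is not sustained, with normal bilirubin and INR and no symptoms, meets no item on that list.
- *Shift tables.* These use normal, high and low. ALT of 1.1x ULN and of 6x ULN fall in the same high cell.
- *Minimum and maximum.* These can show that one extreme value exists, but not how many subjects passed a threshold.
- *Listing of abnormal values.* It gives no counts by arm.
- *Creatinine clearance.* It is not in the chemistry panel (Protocol 6.4.1.13), and the derived data in SAP 5.2.1 do not include it. It therefore appears in no laboratory summary that the SAP describes.

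**4. Can serum creatinine stand in for clearance?** Protocol Appendix 2 gives clearance = (140 − age) x ideal weight / (72 x creatinine), times 0.85 for women. With age and height fixed, a 50% fall is a creatinine of 2.0x baseline. After d years the ratio is 2 x (140 − age − d)/(140 − age). At age 40 this is 2 x 99/100 = 1.98 after 1 year and 2 x 97/100 = 1.94 after 3 years. So a subject whose baseline creatinine is at or below half the ULN can meet the criterion and stay normal in the shift table.

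Example (assumed subject): a woman aged 40, 165 cm.
- Ideal weight = 45.5 + 2.3 x (165 − 152.4)/2.54 = 56.9 kg.
- Creatinine 0.6 mg/dL: 100 x 56.9/(72 x 0.6) x 0.85 = 112.0 mL/min.
- Creatinine 1.2 mg/dL: 56.0 mL/min, a fall of 50.0%.

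The documents give no reference range. If the ULN is 1.2 mg/dL or higher, there is no shift. If it is lower, she moves to high and shares that cell with anyone just above the limit.

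**5. Effect of the recheck label** (assumed values). Neutrophils are 0.9 at Week 12, and the recheck is 1.6 (x10⁹/L).
- Recheck labelled unscheduled: 3.1 leaves it out, the Week 12 value is 0.9, and the subject is counted.
- Recheck labelled Week 12: 3.1.4 selects 1.6, and the subject is not counted.
- A value of 0.9 found only at an unscheduled visit is not counted at all.

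To show the possible size, suppose k subjects cross a threshold at a scheduled visit, a share q return to the other side on recheck, and a share f of rechecks carry the visit label. The table then shows k x (1 − q x f). With k = 10 and q from 0.3 to 0.7, it shows 10 when f = 0, and 7 down to 3 when f = 1. These inputs are assumptions, because the documents give none of them.

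**The case against.** The case for leaving the plan alone has several parts.

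- *The 7.2 list is open, and four of its five thresholds are given as examples.* Protocol 8.6.3 sets no thresholds and does not itself cite 7.2. This stands to the extent that five is a minimum, not a closed denominator. But Protocol 7.1.4 and 8.6.1.1 refer the same term to 7.2, and the SAP used that section's exact figures for three of its entries.
- *Liver and kidney data are reported elsewhere.* This is true, and it limits what is at stake. SAP 3.4 also promises summaries of notable laboratory results in general terms, and the table specifications are in a separate document not available here. Yet the only criteria stated in the SAP are the three in 3.4.3.1.
- *The latest-result rule is stated, reasoned and backed by full listings.* It is a fair choice for means. Protocol 7.2 asks for two sequential low counts before AESI reporting, so leaving out unconfirmed values is defensible. It does not justify letting the label decide. The label also matters only when the first value and the recheck fall on opposite sides of the threshold.
- *This is a descriptive, synoptic report of a terminated study.* That may explain a narrower scope, but Protocol 8.1 still asks for the change to be described.

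A reader might also infer that the SAP misdefines its laboratory AESI category. The documents do not support this: the category name is the protocol's own, in 7.1.4 and 8.6.1.1.

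**Conclusion.** The point holds as an undeclared omission plus a counting rule that is not robust. Two of the five abnormalities named in Protocol 7.2 have no threshold count by arm in any output that the SAP describes. The three that remain have counts that can change with a CRF label, and they miss values found only between scheduled visits.

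This rests on three assumptions: that 8.6.3 uses the term as 7.2 does, that the unseen table specifications follow the SAP text, and that sites may label a recheck either way.

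A reader might infer that liver or kidney harm would be hidden. The documents do not support that: adverse events, descriptive statistics, shifts and listings all remain. Nor do they show how many subjects are affected, since they give no abnormality rates and no CRF. The point does not invalidate the study. It should be corrected because safety is the study's whole purpose.

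**What to change.** Make the changes in the body of SAP 3.4.3.1, because SAP section 1 says that the appendices are not a formal part of the signed plan.

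1. Add two criteria to the by-visit table: AST or ALT above 3x ULN, and a creatinine clearance fall of at least 50% from baseline.
2. State the clearance derivation there, using the Protocol Appendix 2 formula. Take the last pre-dose value as baseline. Include a value from the preceding study within 14 days where Day 1 testing was not repeated, as footnote a of the schedule allows.
3. Beside the by-visit table, add a count by arm and overall of subjects with any post-baseline value meeting each of the five criteria. Use scheduled and unscheduled results, as a stated exception to 3.1 and 3.1.4.
4. If a criterion is deliberately left out, say so in the same section and give the reason.

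The cost is a few sentences and a little programming. AST, ALT and creatinine are collected under Protocol 6.4.1.13. Age, sex and height are already in the SAP's demographic table. No procedures or patients are added. The one drawback is that the new count includes single values that a recheck did not confirm, and a table footnote can say so.
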